7.5 Sample Size

Based on database characterization conducted prior to this protocol, the eight databases mentioned above include between 1,417 to 124,221 diagCOVID-19 and labCOVID-19 patients per database, and a total of 153,759 patients, only one database observing hospitalized patients (around 2,000 patients).

The number of patients in each of the proposed EU countries is projected to be modest, but it is difficult to confirm and likely to vary between data sources. As the primary objective is a descriptive one, the aim is to observe a sufficient number of patients in order to estimate the frequency of drug utilization measures with an acceptable level of precision. The 95% CI width will provide an indication of precisions of the point estimate; the upper and lower limit will provide a range of credible values consistent with observed data.

7.6 Data Management

Data management for this study will be conducted using standard IQVIA processes. Further details on the data handling procedures will be provided to the EMA in the SAP and/or in the Data Management Plan. The process would take into consideration any data governance imposed on the data source including any plans to handle the data outside of the institution or country of origin. IQVIA will adhere to all local and regional laws on data protection and privacy.

7.7 Data Analysis

Continuous variables will be described using mean, standard deviation, median, first and third quartiles, minimum, and maximum. Categorical variables will be described by the number and percentage of patients in each category. The number of patients with missing data for each variable will be reported. Confidence intervals (CIs) of 95% will be presented for means using a normal approximation and for proportions using a binomial approximation. Only available data will be summarized.

In all regression analyses, guidelines for appropriate fitting of any logistic or Cox regression model recommend a minimum of 10 outcome events per term (where term may be any linear covariate, non-linear predictor, or interaction term). If sensitivity analyses are to be conducted, fully adjusted regression analysis will only be undertaken if sufficient outcome events are observed. In any scenario where the fully adjusted regression model does not have sufficient events, but a minimally adjusted regression model including only the exposure, age, and sex in the linear predictor does have sufficient events, the minimally adjusted regression model will be carried out instead.

Additionally, in all analyses where Cox regression modelling is used, the hazard rate (HR) can be used to represent the incidence rate.

The results for each country and database will be presented separately.

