7.4 Data Sources

Longitudinal Patient Database (LPD) Belgium (IQVIA)

LPD Belgium is a computerised network of general practitioners (GPs) who contribute to a centralised database of anonymised data of patients with ambulatory visits. Currently, around 300 GPs from 234 practices are contributing to the database covering 1.1M patients from a total of 11.5M Belgians (10.0%). The database covers a time period from 2005 through the present. Observation time is defined by the first and last consultation dates. Drug information is derived from GP prescriptions. Drugs obtained over the counter by the patient outside the prescription system are not reported. No explicit registration or approval is necessary for drug utilisation studies.

Longitudinal Patient Database (LPD) France (IQVIA)

LPD France is a computerised network of physicians including GPs who contribute to a centralised database of anonymised patient EMR. Currently, >1200 GPs from 400 practices are contributing to the database covering 7.8M patients in France. The database covers a time period from 1994 through the present. Observation time is defined by the first and last consultation dates. Drug information is derived from GP prescriptions. Drugs obtained over the counter by the patient outside the prescription system are not reported. No explicit registration or approval is necessary for drug utilisation studies.

Disease Analyser (DA) Germany (IQVIA)

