SIDIAP is collected from EHR records of patients receiving primary care delivered through Primary Care Teams (PCT), consisting of GPs, nurses and non-clinical staff. The Catalan Health Institute manages 286 out of 370 such PCT with a coverage of 5.6M patients, out of 7.8M people in the Catalan population (74%). The database started to collect data in 2006. The mean follow-up is 10 years. The observation period for a patient can be the start of the database (2006), or when a person is assigned to a Catalan Health Institute primary care centre. Date of exit can be when a person is transferred-out to a primary care centre that does not pertain to the Catalan Health Institute, or date of death, or date of end of follow-up in the database. Drug information is available from prescriptions and from dispensing records in pharmacies. Drugs not prescribed in the GP setting might be underreported; and disease diagnoses made at specialist care settings are not included. Studies using SIDIAP data require previous approval by both a Scientific and an Ethics Committee (9).

Hospital de Madrid (HM) Hospitales (Spain)

Hospital de Madrid (HM) Hospitales data are made available through partnership with SIDIAP. The HM Hospitales database covers in-patient care delivered across a network of private hospitals in Spain. HM Hospitales covers more than 17M patients, out of whom a subset will be catalogued and followed for acute care delivered for suspected COVID-19 onset. This database covers more than 2300 confirmed COVID-19 cases and all in-patient hospital care, including the data of admission, conditions, procedures and medicines dispensed in hospital, date of discharge, and date of known death or date of end of follow-up in the database. Studies using HM Hospitales data require review and approval from data custodians at SIDIAP authorised to execute observational network analyses. The number of newly diagnosed patients in each database per month since the outbreak of COVID-19 can be derived from the databases.

None of the databases, except SIDIAP have linkage between primary and secondary care setting.

A database profiling, describing a range of variables in terms of data quality and completeness, as well as attrition tables for COVID-19 populations can be found at the following link:

https://dqdashboard.iqvia.com/ema_report1/.

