7.7.2 Glucocorticoid prescribing patterns (primary objective 1)

Prescribing patterns of systemic glucocorticoids for the treatment of COVID-19 will be summarized by the four cohorts (section 7.2.2) and by subgroups of special interest (section 7.2.4) and the description will include time to initiation of glucocorticoid treatment (from COVID-19 diagnosis), duration of treatment, route of administration, daily dose at start, cumulative dose and duration of

treatment received post COVID-19 diagnosis, see section 7.3.2 for details regarding calculation of exposure parameters .

Frequency of concomitant use of other medications and invasive/non-invasive respiratory support at COVID-19 diagnosis index date and during follow-up will also be presented.

The time to systemic glucocorticoid initiation from COVID-19 diagnosis will be modelled as a time-to-event outcome using the Kaplan-Meier (KM) estimator. The patient follow-up from COVID-19 diagnosis date until systemic glucocorticoid treatment index date will be included in the KM analysis, with start of systemic glucocorticoid therapy being considered a ‘failure’ event. This KM analysis will be stratified by route of systemic glucocorticoid administration (oral vs intravenous). The KM survival function curve (95% CI) and summary statistics of 25th percentile, median, 75th percentile of time to event (in days) will be provided. The survival function within each stratification will be compared using log-rank test.

A time series graph will be used to investigate changes in prescribing patterns over calendar time. Monthly and quarterly incidence steroid incident use will be plotted against time from January 2020 until study end. Key dates (such as Recovery trial) should be highlighted on this graph to allow differentiation between time periods. A formal before /after analysis is not proposed. Results will be stratified per country and per database.

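### The 95% CIs for prescribing measures treat patients as independent although ambulatory patients are nested in practices, teams or providers, so reported precision will be too favourable by an amount that depends on an unstated ICC

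*Protocol*

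**What the plan says.** Protocol section 7.7 fixes the interval method for the descriptive results: "Confidence intervals (CIs) of 95% will be presented for means using a normal approximation and for proportions using a binomial approximation". Results are reported for each database separately.

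Section 7.5 gives no target width and no sample-size calculation. It relies on the interval itself: "The 95% CI width will provide an indication of precisions of the point estimate". It reports that "the eight databases mentioned above include between 1,417 to 124,221 diagCOVID-19 and labCOVID-19 patients per database, and a total of 153,759 patients", without saying which database holds the maximum.

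Section 7.4 describes the ambulatory sources by contributing unit. For LPD Belgium, "around 300 GPs from 234 practices are contributing to the database". For SIDIAP, "The Catalan Health Institute manages 286 out of 370 such PCT with a coverage of 5.6M patients". The others are LPD France (400 practices), IPCI (391 GPs), IMRD UK (793 care sites), LPD Italy (900 practices) and DA Germany (2,734 providers, specialists included).

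Section 7.7.2 adds for time to initiation: "The KM survival function curve (95% CI) and summary statistics of 25th percentile, median, 75th percentile of time to event (in days) will be provided". No section mentions clustering, a design effect, a robust variance or practice effects. The random-effects model in 7.7.7 covers only variation of hazard ratios between databases.

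**The concern.** The primary objective describes what prescribers do: whether a systemic glucocorticoid is started, which one, by what route, at what starting dose, for how long and how soon. Patients of the same practice or team are treated by the same few prescribers under the same local habits. Their outcomes are therefore likely to be positively correlated, and each additional patient from a practice adds less information than an independent patient would. The binomial and normal intervals ignore this.

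The study has no power statement and no precision target, so the interval is its whole statement of uncertainty. If clustering is ignored, a nominal 95% interval covers less than 95%. The shortfall grows with the number of cases per practice, so it is largest in the database that appears most precise.

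**Working it through.** The protocol states no precision figure, so there is none to reproduce. The check asks how far the specified interval departs from one that allows for clustering.

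**Inputs from the protocol.** 124,221 cases in the largest database, 1,417 in the smallest, 153,759 in total and about 2,000 in the hospital database (7.5); cluster counts as listed above (7.4).

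**Assumptions.** ICC 0.001 to 0.10, since none is given. The largest database is SIDIAP. Clusters are of equal size. 5% of patients are treated, where a treated subset is needed.

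**Formulas.** With m = cases / clusters, the design effect is DEFF = 1 + (m − 1) × ICC. The specified interval is too narrow by a factor of √DEFF. Its actual coverage is 2Φ(1.96/√DEFF) − 1.

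**Largest database, whole cohort.** m = 124,221 / 286 = 434.3.

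| ICC | DEFF | Too narrow by | Coverage |
|---|---|---|---|
| 0.001 | 1.43 | 1.20 | 90% |
| 0.01 | 5.33 | 2.31 | 60% |
| 0.05 | 22.67 | 4.76 | 32% |
| 0.10 | 44.33 | 6.66 | 23% |

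**If another database is the largest.** With DA Germany's 2,734 providers, m = 45.4. DEFF is 1.44, 3.22 and 5.44 at ICC 0.01, 0.05 and 0.10, and coverage is 90%, 72.5% and 60%. With LPD Belgium's 234 practices, m = 530.9. DEFF is 27.5 at ICC 0.05 and 54.0 at ICC 0.10, somewhat worse than SIDIAP.

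**If the target is only Catalonia.** The 286 teams are part of 370, so a finite-population factor of 1 − 286/370 = 0.227 applies, taking the recorded patients of each team as fixed. At ICC 0.01, 0.227 × 5.33 = 1.21 and coverage is about 92%. At ICC 0.05, 0.227 × 22.67 = 5.15 and coverage is about 61%. On this view the simple interval is too narrow only when 0.227 × (1 + 433.3 × ICC) exceeds 1, that is, when the ICC is above about 0.008.

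**Treated-only measures (type, route, dose, duration).** 5% of 124,221 is 6,211 users, so m = 6,211 / 286 = 21.7. DEFF is 1.21, 2.04 and 3.07 at ICC 0.01, 0.05 and 0.10, and coverage is 93%, 83% and 74%.

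**Smaller databases.** The other six ambulatory databases average (153,759 − 124,221 − 2,000) / 6 = about 4,590 cases. At ICC 0.05, 234 sites give DEFF 1.93 and coverage 84%; 400 sites give DEFF 1.52 and coverage 89%. For 1,417 cases in 234 practices, m = 6.1, DEFF is 1.25 and coverage is 92%.

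**Absolute size.** At 5% use in the largest database, the simple half-width is 1.96 × √(0.05 × 0.95 / 124,221) = 0.12 percentage points. At ICC 0.05 it becomes 0.12 × 4.76 = about 0.58 points.

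**Simulation.** A beta-binomial simulation (3,000 runs, 5% use, ICC 0.05, unequal cluster sizes) gave simple-interval coverage of 27.9% for 124,221 cases in 286 clusters, 64.8% in 2,734 clusters, and 88.8% for 1,417 cases in 234 clusters. The cluster-robust interval covered 94.1% to 95.2% in the simulated settings.

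**The case against.** The strongest reply is that the size rests on an assumed ICC. That stands. At 5% use, ICC 0.05 implies a between-team standard deviation of √(0.05 × 0.95 × 0.05) = 4.9 percentage points, with team rates running from roughly 0.2% to 15% (5th to 95th percentile, beta model). That is wide variation. A SIDIAP team also pools several prescribers and about 5.6M / 286 = 19,600 patients, which may dilute the correlation that comes from individual habit. At ICC 0.001, coverage is still about 90%.

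The target matters too. If the results describe only the recorded patients, the argument weakens. If they describe Catalonia, the finite-population figures above apply. The protocol's stated aim, however, covers care in seven countries, and it presents the IPCI selection of GPs as representative of the Netherlands. An interval on such results is read as inference beyond the recorded patients.

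It may also be said that variance details belong in the SAP, which is not at hand. But the protocol itself names the interval method and rests its precision on it.

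Stronger readings that a reader might infer are not supported:

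- That a stated precision is wrong. Section 7.5 gives no figure.
- That every database consists of a few hundred GP practices. DA Germany has 2,734 providers, IMRD UK and LPD Italy have 793 and 900 units, and HM Hospitales is a hospital network of unstated size.
- That false differences between groups will drive conclusions. Comparative assessment is out of scope, subgroups are not for statistical comparison, and no formal before/after analysis is planned. The log-rank test by route in 7.7.2 is the exception; it was not quantified here.
- That the standard errors pooled in 7.7.7 are shown to be affected. Those concern outcome hazard ratios, and no calculation was made for them.

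**Conclusion.** The point holds in a limited form. The specified intervals assume independence that the protocol's own description of its data sources makes doubtful, and their width is the study's only measure of precision. Where practices stand for a wider set of prescribers, any positive within-practice correlation makes the intervals too narrow.

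The direction is clear but the size is not. It depends on the ICC, on which database is the largest and on the target population, none of which the protocol settles. Calling the error severe is justified only for whole-cohort proportions in the largest database, at an ICC of about 0.01 or more, and with inference beyond Catalonia. For treated-only measures and the smaller databases it is small to moderate. Even in the largest database the absolute widths stay small, so the practical harm is an interval labelled 95% that may cover much less. It does not make the prescribing estimates unusable.

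**What to change.** In 7.7, for the ambulatory databases, compute the intervals for proportions (on the logit scale) and for means with a cluster-robust variance or a cluster bootstrap. Use the practice, care site, team or provider as the cluster wherever that identifier exists. Do the same for the Kaplan-Meier intervals in 7.7.2. Where no identifier exists, keep the simple interval and label it as assuming independent patients. In 7.5, state that precision is judged on the clustered interval.

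The cost is wider intervals and slightly more analysis work, done locally in each database in line with the protocol's model of local analyses. The protocol does not show that identifiers are available in every analysis dataset, which is why the labelled fallback is needed. Point estimates do not change, and no further patients or data collection are required.

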- Spain – Information System for Research in Primary Care (SIDIAP) as primary care databases

Hospital:

- Hospital de Madrid Hospitales

Data analysis

Continuous variables will be described using mean, standard deviation, median, first and third quartiles, minimum, and maximum. Categorical variables will be described by the number and percentage of patients in each category. Patterns of missingness will be reported and 95% confidence Intervals will be presented. The

results for each country and where available, each setting will be presented separately.

Primary Objective:

- Descriptive analysis for systemic glucocorticoid use patterns will be carried and stratified by setting, glucocorticoid exposure type (naive, prevalent) and subgroups of special interest.
- Kaplan-Meier methods will be used to estimate time to systemic glucocorticoid initiation from COVID-19 diagnosis, stratified by route of administration (oral vs intravenous).

Secondary Objective 1:

- Cohort-specific descriptive statistics summarizing demographic, health and clinical patient characteristics, stratified by setting, glucocorticoid exposure type glucocorticoid (naive, prevalent), and subgroups of special interest will be presented.

Secondary Objectives 2 and 3:

- Crude incidence (presented as both proportions and rates) for the relevant outcomes for each of the treatment exposure groups will be calculated.
- The cumulative incidence rates will be reported at the end of follow-up (30 and 90 days).
- Data will be stratified by setting, glucocorticoid exposure type (naive, prevalent), and subgroups of special interest
- Cox regression models (using multivariable models and using PS adjustment) will be used to compute the adjusted incidence rates.

Secondary Objective 4:

- The performance of different COVID-19 disease definitions based on rule-based phenotype algorithms will be explored using diagnostic predictive modelling

**Plans for
Disseminating
and
Communicating
Study Results**

IQVIA will produce a study report in accordance with the GVP guidelines VIII (EMA/813938/2011). Study information (including protocol and final report) will be added in the EU PAS register.

Section 3.0 Amendments and Updates

Major and Minor Amendments	
Major Amendments	Minor Amendments

 None 	
 Abstract section Appendix 3 Misspellings and editorial checks across the entire document

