6.3 Secondary Objectives

1. To describe **at COVID-19 diagnosis date and at treatment index date** the demographic, health and clinical patient characteristics. The following variables will be described:
 - demographics
 - comorbidities (number and type)
 - symptoms (number and type) preceding and/or on the date of diagnosis the diagnosis if captured time from onset of COVID-19 illness symptoms to confirmed diagnosis date.

Some of these characteristics will be stratified by setting, glucocorticoid exposure type (naive, prevalent) and subgroups of special interest. (e.g., chronic cardiac and pulmonary disease, diabetes, renal insufficiency, see Section 7.2.4 Subgroups).

2. To quantify the crude and adjusted (selected confounders tbc) incidence rates and time to onset of adverse events of interest (e.g., infections, hyperglycaemia, hypertension, GI bleeding, composite of cardiovascular events) within **30 and 90 days post treatment index date**, in **various treatment groups**, stratified by setting, glucocorticoid exposure type (naive, prevalent) and subgroups of special interest.

3. To quantify the crude and adjusted incidence rates of mortality and other disease outcomes within **30 and 90 days post treatment index date**, in **various treatment groups**, stratified by setting, glucocorticoid exposure type (naive, prevalent) and subgroups of special interest.

4. To explore the performance of **different coding definitions** for COVID-19 and how they influence the size of the cohort

Out of scope:

To assess comparative effectiveness and safety between individual treatments administered for COVID-19 infection or between treated and untreated patients.

To validate definition for COVID-19 using clinical adjudication of individual patient medical records sampled from the study population

[figure not shown]
Section 7.0 Research Methods

[figure not shown]
[figure not shown]

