For each sub-cohort and type of person-time the numerator for each time frame will contain the number of patients for whom an outcome has been recorded in that time frame since the onset of that type of person-time. The crude incidence rate of each outcome within the relevant sub-cohort will be expressed as number of cases per 1,000 patient-days at risk.

The cumulative incidence rate will be reported at the end of follow-up (30 and 90 days).

The person-time estimation and the calculation of the crude incidence rate for secondary objectives 2 and 3 will be similar except for the outcomes being considered in each case. For secondary objective 2, adverse events of interest for glucocorticoids (listed in Section 7.3.3) will be the outcome, and for secondary objective 3 mortality and other disease outcomes (Section 7.3.4) will be the outcome.

Both stratification and adjustment will be used as a method to deal with confounders.

In order to examine risk factors of the outcomes of interest, data will also be stratified by subgroups of interest (7.2.4) and stratum-specific crude incidence rates will be calculated. The stratification variables include the healthcare setting, glucocorticoid user type (naive, prevalent) treatment groups and subgroups of special interest.

Separate Cox regression models will be used to estimate adjusted cause-specific HR³ (in order to account for competing events) for each outcome **within** the following four treatment groups:

- Use of systemic glucocorticoids without other treatments for COVID-19 (drug and respiratory support)
- Use of systemic glucocorticoids plus other treatments for COVID-19 (drug and respiratory support)
- Only other treatments and respiratory support with no systemic glucocorticoids

³ Cause-specific HR are to be interpreted as instantaneous risk estimates and not as cumulative risk estimates; cumulative risks estimates are subject to competing events <https://pubmed.ncbi.nlm.nih.gov/30012114/>

- No specific treatments for COVID-19 infection (other concomitant treatments for indications other than for COVID-19 are allowed)

In addition to stratified analysis, for each of the above four treatment groups, two sets of Cox regression models will be run:

- 1) A model that is adjusted for a list of predefined confounders
- 2) A model that is adjusted for a high dimension propensity score that is derived through large-scale modelling, using all available covariates in each dataset (Section 7.7.5)

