7.7.5 High dimension propensity score

The primary confounding adjustment strategy that will be employed is propensity score adjustment through large-scale modelling, using all available demographics, clinical conditions, and drug groupings in the 30 days and 365 days pre-index intervals as baseline covariates. (26,27) The complete list of covariates that will be used to calculate the propensity score are the 'OHDSI covariates' as described in the publication by Tian et al. (2018) (27)

Propensity scores will be calculated using L1-regularisation (i.e. LASSO regression) using all 'OHDSI covariates' (listed in Tian et al., 2018) to predict the treatment exposure of interest by penalizing the loss function to help simplify the model specification and to avoid overfitting. This approach of using L1-regularisation has been shown to achieve more robust treatment prediction and covariate balance when compared to a high-dimensional propensity score model. (27) The PS will be then included in the Cox model as an independent variable, to obtain adjusted the incidence rates.

An added advantage of using propensity scores in a regression model, rather than individual covariate adjustment, is that propensity scores are more robust when dealing with rare outcomes (28)

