7.7.7 Meta-analysis

All the proposed analyses will be conducted for each database separately, with cumulative HR estimates (at 30 days follow-up) for each treatment group of interest combined using the DerSimonian-Lard random effects meta-analysis methods when $I^2 \leq 40\%$. The standard errors associated with the cumulative HRs will be used to weight individual database estimates using the inverse variance weighting methods. No meta-analysis will be conducted when I^2 for a given drug-outcome pair is $>40\%$.

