7.7.8 Sensitivity analysis

For objective 2 and 3, with regards to the reference group for incidence rates

As a sensitivity analysis, the reference group for incidence rates will be replaced with ‘other immunotherapies’ (see Appendix 3 for details).

For prevalent users’ cohorts, the definition of remote users:

A sensitivity analysis to exclude those patients for whom short term duration of corticosteroid use (14 days) is identified prior to COVID-19 diagnosis.

For objectives 2 and 3, if the number of patients censored due to switching is higher than 70%, a sensitivity analysis will be performed, namely an intention to treat approach (ITT), such that after initial exposure is defined to allocate patients to one of the four treatment groups, the denominator is then person-time observed (irrespective of treatment status), rather than person-time treated.

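### The adjusted incidence rates of secondary objectives 2 and 3, and the quantity pooled across databases, are not defined as written, and the rule equating a Cox HR with an incidence rate is wrong

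*Protocol*

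**What the plan says.** - **Target.** Protocol section 6.3, objective 3: "To quantify the crude and adjusted incidence rates of mortality and other disease outcomes". Objective 2 promises the same for adverse events. The abstract (Section 2.0, Data analysis) says how: "Cox regression models (using multivariable models and using PS adjustment) will be used to compute the adjusted incidence rates".
- **Bridge from model to target.** Section 7.7: "in all analyses where Cox regression modelling is used, the hazard rate (HR) can be used to represent the incidence rate".
- **Model.** Section 7.7.4 estimates adjusted cause-specific HRs separately inside each treatment group, with the word within in bold: "In addition to stratified analysis, for each of the above four treatment groups, two sets of Cox regression models will be run". One set adjusts for predefined confounders, the other for a propensity score. Footnote 3 there says such HRs are instantaneous and not cumulative risk estimates.
- **Fallback model.** If events are too few, section 7.7 substitutes a model with exposure, age and sex.
- **Propensity score.** Section 7.7.5 uses a LASSO model to predict the treatment exposure, then: "The PS will be then included in the Cox model as an independent variable, to obtain adjusted the incidence rates".
- **Pooling.** Section 7.7.7 has "cumulative HR estimates (at 30 days follow-up) for each treatment group of interest combined using the DerSimonian-Lard random effects meta-analysis methods".
- **Sensitivity analysis.** Section 7.7.8: "the reference group for incidence rates will be replaced with" other immunotherapies.
- **Scope.** Section 6.3 lists as out of scope: "To assess comparative effectiveness and safety between individual treatments administered for COVID-19 infection or between treated and untreated patients". Section 7.9.1 repeats that no comparative analysis will be done.

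**The concern.** The target is an absolute quantity per treatment group, and section 7.7.4 expresses the crude rate in events per 1,000 patient-days. The planned model output is a ratio between patients who differ in a covariate. The sentence in section 7.7 treats the two as interchangeable, and later sections build on it: the propensity score is said to deliver adjusted rates, and the meta-analysis pools one HR per treatment group.

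This is more than detail left to a statistical analysis plan. The protocol fixes the model, the stratum in which it is fitted, the claimed meaning of its output and the pooled quantity, and these do not fit together. An analysis plan that followed the protocol faithfully would inherit the error. If HRs were tabulated as rates, the adjusted safety and mortality figures in the final report would be wrong.

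**Working it through.** The protocol gives no adjusted rate, expected rate or precision target to reproduce. The check is therefore algebra, plus a simulation with assumed inputs.

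**1. What a Cox fit inside one group estimates.** With hazard h(t|x) = h0(t)·exp(βx), each event contributes to the partial likelihood

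exp(βx_i) / Σ_j exp(βx_j), summed over those still at risk.

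The baseline h0(t) cancels. The output is exp(β), a ratio with no time unit. The absolute level sits in h0(t), which this likelihood does not estimate.

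**2. Does the HR follow the rate?** Assumptions: one group of 6,000 patients, 30-day follow-up with random earlier censoring, true HR 1.65 per SD of age and 1.35 for sex. The baseline hazard was set at three levels.

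| Baseline hazard per 1,000 patient-days | Events | Crude rate per 1,000 patient-days | HR age | HR sex |
|---|---|---|---|---|
| 1 | 167 | 1.19 | 1.47 | 1.16 |
| 3 | 508 | 3.80 | 1.53 | 1.16 |
| 10 | 1,525 | 12.73 | 1.64 | 1.40 |

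The crude rate rises by a factor of 12.73/1.19 = 10.7. The HRs estimate the same two ratios throughout, and their differences are sampling error. In a further simulated data set, measuring time in days, weeks or hours left the age HR at 1.6613 each time, while the crude rate went from 0.00321 to 0.02244 to 0.00013 per unit of time. A number that does not change with the time unit cannot be a rate.

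**3. Is there a treatment term?** Inside one group the exposure is the same for everyone. Its factor exp(γ) stands in the numerator and in every term of the denominator of step 1, and cancels. Numerically, the information matrix for exposure plus age had rank 1 of 2. So no treatment HR exists within a group, and the exposure term of the fallback model in 7.7 cannot be estimated there.

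**4. What the propensity score adds.** Entered as a covariate, it yields one more ratio, for the score. That alone gives no adjusted rate. Section 7.7.5 also does not say which contrast among the four groups the score models.

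**5. What would give an absolute figure.** Take the same within-group fits, add a Breslow cumulative baseline H0(30), and compute

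- reference-level rate = 1,000·H0(30)/30
- standardised 30-day risk = mean over patients of 1 − exp(−H0(30)·exp(βx)), with no competing event simulated.

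| True baseline rate per 1,000 patient-days | Reference-level rate recovered | Standardised 30-day risk (true) |
|---|---|---|
| 1 | 1.06 | 0.036 (0.039) |
| 3 | 3.21 | 0.106 (0.111) |
| 10 | 9.87 | 0.316 (0.315) |

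An adjusted absolute measure is obtainable, but only with steps the protocol does not name.

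**6. Downstream text.** Section 7.7.7 needs one estimate with a standard error per group and database; steps 1 to 4 supply none. A cumulative HR also sits badly with footnote 3 of 7.7.4. Section 7.7.8 replaces a reference group that the main analysis never defines, in a study that excludes comparison.

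**The case against.** The best defence turns on the abbreviation. Section 7.7 expands HR as hazard rate, and footnote 3 calls the HRs instantaneous risk estimates. On that reading the cumulative HR at 30 days in 7.7.7 could mean a cumulative hazard: one value per group and database, with a standard error. Step 5 shows that such a value can be had from a within-group Cox fit, and a statistical analysis plan, not shown here, might supply the missing step. This stands as far as it goes: a reader might infer that Cox models cannot yield a rate, or that the meta-analysis is impossible, and the documents do not support either. It does not rescue the text. Adjusted cause-specific HR in 7.7.4 is the usual term for a ratio, and on either reading no baseline estimate, covariate values or standard population is given.

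It would also be too strong to say that the propensity score is useless. Section 7.7.5 does not say it is estimated inside one group; a score fitted across groups varies within each, and predictions could be averaged over a chosen score distribution. Within-group covariate HRs also have a legitimate use in examining risk factors, which 7.7.4 mentions.

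Finally, the simulation demonstrates a general property of Cox models. It does not measure an error in this study.

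**Conclusion.** The point holds in a limited form. The section 7.7 sentence is wrong for the HRs that 7.7.4 produces, and the adjusted rates of objectives 2 and 3, the quantity pooled in 7.7.7 and the reference group in 7.7.8 are undefined as written.

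The extent is every adjusted result of these two secondary objectives, in all four treatment groups and every database, plus the whole meta-analysis. No numerical bias can be given, because the protocol states no expected rates.

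A reader might also infer that objectives 2 and 3 fail altogether. They do not: crude rates and incidence proportions have their own formulas in 7.7.4, stratified rates follow from the crude method, and the primary objective uses none of these models.

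Steps 1 and 3 are algebraic and need no assumed values. The figures in steps 2 and 5 rest on the assumed hazards and covariate effects.

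**What to change.** Before analysis:

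1. **Section 7.7:** delete the sentence equating HR with the incidence rate, and remove exposure from the fallback model wherever it is fitted within one group.
2. **Section 7.7.4:** define the adjusted result for each treatment group as an absolute quantity. Two suitable options are a covariate-standardised rate per 1,000 patient-days from a piecewise Poisson or flexible parametric model, or a standardised 30- and 90-day cumulative incidence from Cox with an estimated baseline hazard and the competing-event hazards. State the standard population.
3. **Section 7.7.5:** state which contrast the propensity score models and how it is used, for example as weights, with a check of overlap.
4. **Section 7.7.7:** pool that same quantity with its standard error on a suitable scale, such as the log rate.
5. **Section 7.7.8:** define the reference group, or reconcile the analysis with the non-comparative scope.

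A single joint model for all four groups, standardised to the whole cohort, is possible but not required. It fits less well with the within-group design and the exclusion of comparisons.

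**Cost:** rewording of these sections and the abstract line, and some recoding; no new data. The downside is that standardising to a population outside the group depends on covariate overlap. Overlap may be limited, since section 7.9.1 itself expects glucocorticoid use to follow disease severity.
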